5.5.2 Dose Limiting Toxicities (DLTs)

DLT is defined as any of the following that occur during the time frame between the first dose of MK-3475 and 3 weeks after the second dose of MK-3475 that are attributed as possibly, probably, or definitely related to the study treatment:

- Grade 2 or greater diarrhea
- Autoimmune hypophysitis
- Grade 3 or greater hepatitis
- Grade 2 or greater pneumonitis
- Significant intracranial edema requiring high-dose steroid (defined as > 16 mg/day and/or inability to taper steroids to ≤ 8 mg/day within 4 weeks due to recurrent symptoms attributable to excessive cranial edema)
- Grade 3 or greater non-hematologic toxicity
- Grade 3 or greater hematologic toxicity

5.5.3 Dose Escalation Criteria

Dose escalations will proceed as follows after the occurrence of DLT:

Number of Patients with DLT at a Given Dose Level	Escalation Decision Rule
0 out of 3	Enter 3 patients at the next dose level
2 or 3 out of 3	Dose escalation will be stopped and 3 patients will be entered at the next lowest dose level if only 3 patients were treated previously at that dose.
1 out of 3	
 • Enter at least 3 more patients at this dose level. • If 0 of these 3 patients experience DLT, proceed to the next dose level. • If 1 or more of this group suffer DLT, then dose escalation is stopped and 3 additional patients will be entered at the next lowest dose level if only 3 patients were treated previously at that dose.
≤ 1 out of 6 at highest dose level below the maximally administered dose	This is generally the recommended phase II dose. At least 6 patients must be entered at the recommended phase II dose.

5.6 Toxicity, Response, and DLT Evaluations

All patients who receive any treatment with MK-3475 are evaluable for toxicity. Patients are evaluated from first receiving study treatment until a 30-day follow-up after the conclusion of treatment or death.

All phase II patients are evaluable for disease response unless they come off study before any disease assessment.

A phase I patient is evaluable for DLT assessment from the time of the first dose of MK-3475 through 3 weeks following the second dose of MK-3475. Once the patient has received his/her third dose of MK-3475, s/he will no longer be evaluated for DLTs. Patients who do not incur a DLT and who receive only a single dose of MK-3475 or who do not undergo MLA should be considered not evaluable for DLT and should be replaced.

5.7 General Concomitant Medication and Supportive Care Guidelines

All treatments that the investigator considers necessary for a patient's welfare may be administered at the discretion of the investigator in keeping with the community standards of medical care.

Patients are prohibited from receiving the following therapies while in screening for and enrolled in this trial:

- Anti-cancer systemic chemotherapy or biological therapy. Treatment with bevacizumab as a steroid-sparing agent is allowed on trial.
- Immunotherapy not specified in this protocol
- Chemotherapy not specified in this protocol
- Investigational agents other than MK-3475
- Radiation therapy
- Live vaccines within 30 days prior to the first dose of treatment and while participating in the trial. Examples of live vaccines include, but are not limited to, the following: measles, mumps, rubella, varicella/zoster, yellow fever, rabies, BCG, and typhoid vaccine.

5.7.1 Supportive Care Guidelines for Infusion Reactions

Pembrolizumab may cause severe or life-threatening reactions including severe hypersensitivity or anaphylaxis. Signs and symptoms usually develop during or shortly after drug infusion and generally resolve completely within 24 hours of completion of infusion.

The table below shows treatment guidelines for patients who experience an infusion reaction associated with administration of MK-3475.

NCI CTCAE Grade	Treatment	Premedication at subsequent dosing
Grade 1 Mild reaction; infusion interruption not indicated; intervention not indicated	Increase monitoring of vital signs as medically indicated until the subject is deemed medically stable in the opinion of the investigator.	None
Grade 2 Requires infusion interruption but responds promptly to symptomatic treatment (e.g., antihistamines, NSAIDS, narcotics, IV fluids); prophylactic medications indicated for <=24 hrs	Stop Infusion and monitor symptoms. Additional appropriate medical therapy may include but is not limited to: IV fluids, antihistamines, NSAIDS, acetaminophen, Narcotics Increase monitoring of vital signs as medically indicated until the subject is deemed medically stable in the opinion of the investigator. If symptoms resolve within one hour of stopping drug infusion, the infusion may be restarted at 50% of the original infusion rate (e.g. from 100 mL/hr to 50 mL/hr). Otherwise dosing will be held until symptoms resolve and the subject should be premedicated for the next scheduled dose. Subjects who develop Grade 2 toxicity despite adequate premedication should be permanently discontinued from further trial treatment administration.	Subject may be premedicated 1.5h (\pm 30 minutes) prior to infusion of MK-3475 with: Diphenhydramine 50 mg po (or equivalent dose of antihistamine). Acetaminophen 500-1000 mg po (or equivalent dose of antipyretic).

NCI CTCAE Grade	Treatment	Premedication at subsequent dosing
Grades 3 or 4 Grade 3: Prolonged (i.e., not rapidly responsive to symptomatic medication and/or brief interruption of infusion); recurrence of symptoms following initial improvement; hospitalization indicated for other clinical sequelae (e.g., renal impairment, pulmonary infiltrates) Grade 4: Life-threatening; pressor or ventilatory support indicated	Stop Infusion. Additional appropriate medical therapy may include but is not limited to: IV fluids, antihistamines, NSAIDS, acetaminophen, narcotics, oxygen, pressors, corticosteroids, epinephrine Increase monitoring of vital signs as medically indicated until the subject is deemed medically stable in the opinion of the investigator. Hospitalization may be indicated. Subject is permanently discontinued from further trial treatment administration.	No subsequent dosing
Appropriate resuscitation equipment should be available in the room and a physician readily available during the period of drug administration.		

5.8 Women of Childbearing Potential

Women of childbearing potential (defined as women with regular menses, women with amenorrhea, women with irregular cycles, women using a contraceptive method that precludes withdrawal bleeding, and women who have had a tubal ligation) are required to have a negative serum or urine pregnancy test within 72 hours prior to the first dose of MK-3475.

Pembrolizumab may have adverse effects on a fetus in utero.

For this trial, male subjects will be considered to be of non-reproductive potential if they have azoospermia (whether due to having had a vasectomy or due to an underlying medical condition).

A woman is considered fertile following menarche and until becoming post-menopausal unless permanently sterile (see below). Women in the following categories are not considered of childbearing potential:

- Premenarchal
- Premenopausal female with 1 of the following:
 - Documented hysterectomy
 - Documented bilateral salpingectomy
 - Documented bilateral oophorectomy

Note: Documentation can come from the site personnel's review of the participant's medical records, medical examination, or medical history interview.
- Postmenopausal female
 - A postmenopausal state is defined as no menses for 12 months without an alternative medical cause.
 - A high follicle stimulating hormone (FSH) level in the postmenopausal range may be used to confirm a postmenopausal state in women not using hormonal contraception or hormonal replacement therapy (HRT). However,

in the absence of 12 months of amenorrhea, confirmation with two FSH measurements in the postmenopausal range is required.

- Females on HRT and whose menopausal status is in doubt will be required to use one of the non-hormonal highly effective contraception methods if they wish to continue their HRT during the study. Otherwise, they must discontinue HRT to allow confirmation of postmenopausal status before study enrollment.

Contraception Requirements

Subjects should be informed that taking the study medication may involve unknown risks to the fetus (unborn baby) if pregnancy were to occur during the study. In order to participate in the study subjects of childbearing potential must adhere to the contraception requirement (described below) from the day of study medication initiation (or 14 days prior to the initiation of study medication for oral contraception) throughout the study period up to 120 days after the last dose of trial therapy. If there is any question that a subject of childbearing potential will not reliably comply with the requirements for contraception, that subject should not be entered into the study.

Male Participants:

Male participants with female partners of childbearing potential are eligible to participate if they agree to one of the following during the protocol defined timeframe:

- Be abstinent from penile-vaginal intercourse as their usual and preferred lifestyle (abstinent on a long term and persistent basis) and agree to remain abstinent
- Use a male condom plus partner use of a contraceptive method with a failure rate of <1% per year as described in the table below when having penile-vaginal intercourse with a woman of childbearing potential who is not currently pregnant.
 - Note: Men with a pregnant or breastfeeding partner must agree to remain abstinent from penile-vaginal intercourse or use a male condom during each episode of penile penetration.

Female Participants

Female participants of childbearing potential are eligible to participate if they agree to use a highly effective method of contraception consistently and correctly as described in the table below during the protocol-defined timeframe.

Highly Effective Contraceptive Methods That Are User Dependent ^a
Failure rate of < 1% per year when used consistently and correctly.

● Combined (estrogen- and progestogen-containing) hormonal contraception ^{b, c}
○ Oral○ Intravaginal○ Transdermal○ Injectable● Progestogen-only hormonal contraception ^{b, c}
○ Oral○ Injectable
Highly Effective Methods That Have Low User Dependency
Failure rate of <1% per year when used consistently and correctly.

 • Progestogen- only contraceptive implant ^{b, c} • Intrauterine hormone-releasing system (IUS) ^b • Intrauterine device (IUD) • Bilateral tubal occlusion

 • Vasectomized partner A vasectomized partner is a highly effective contraception method provided that the partner is the sole male sexual partner of the WOCBP and the absence of sperm has been confirmed. If not, an additional highly effective method of contraception should be used.

 • Sexual abstinence Sexual abstinence is considered a highly effective method only if defined as refraining from heterosexual intercourse during the entire period of risk associated with the study treatment. The reliability of sexual abstinence needs to be evaluated in relation to the duration of the study and the preferred and usual lifestyle of the participant.)

Notes:
 
Use should be consistent with local regulations regarding the use of contraceptive methods for participants of clinical studies.
 
a) Typical use failure rates are lower than perfect-use failure rates (i.e. when used consistently and correctly).
 
b) If hormonal contraception efficacy is potentially decreased due to interaction with study treatment, condoms must be used in addition to the hormonal contraception during the treatment period and for at least [X days, corresponding to time needed to eliminate study treatment plus 30 days for study treatments with genotoxic potential] after the last dose of study treatment.
 
c) If locally required, in accordance with Clinical Trial Facilitation Group (CTFG) guidelines, acceptable hormonal contraceptives are limited to those which inhibit ovulation.

Pregnancy Testing

WOCBP should only be included after a negative highly sensitive urine or serum pregnancy test.

Following initiation of treatment, pregnancy testing will be performed whenever an expected menstrual cycle is missed or when pregnancy is otherwise suspected, after the last dose of study treatment, and as required locally.

Pregnancy testing will be performed whenever an expected menstrual cycle is missed or when pregnancy is otherwise suspected.

5.9 Duration of Therapy

If at any time the constraints of this protocol are considered to be detrimental to the patient's health and/or the patient no longer wishes to continue protocol therapy, the protocol therapy should be discontinued and the reason(s) for discontinuation documented in the case report forms.

In the absence of treatment delays due to adverse events, treatment may continue for up to 24 months (35 cycles; the number of treatments is calculated starting with the first dose) or until one of the following criteria applies:

- Documented and confirmed disease progression
- Death
- Adverse event(s) that, in the judgment of the investigator, may cause severe or permanent harm or which rule out continuation of study drug
- General or specific changes in the patient's condition render the patient unacceptable for further treatment in the judgment of the investigator
- Suspected pregnancy
- Serious non-compliance with the study protocol
- Lost to follow-up
- Patient withdraws consent
- Investigator removes the patient from study
- The Siteman Cancer Center decides to close the study

Patients who prematurely discontinue treatment for any reason will be followed as indicated in the study calendar.

Patients currently on pembrolizumab beyond the 2 year/35 cycle limit at the time of the approval of Amendment 13 may continue to receive pembrolizumab unless there is progression, toxicity or agreement by the patient and PI to come off therapy.

Participants who discontinue pembrolizumab after receiving 35 doses are eligible for retreatment with pembrolizumab if they progress during follow-up provided they meet the requirements detailed in Section 5.10. Participants may receive an additional 17 cycles (12 months) of pembrolizumab during the Second Course Phase (Retreatment).

5.10 Second Course Phase

All participants who discontinue treatment with pembrolizumab with at least stable disease are eligible for 17 further cycles (approximately 1 year) of pembrolizumab if they progress during follow-up. This retreatment is termed the Second Course Phase of this study and is only available if all of the following conditions are satisfied:

1. The study is open at the time the patient qualifies for retreatment.
2. The patient experienced investigator-determined radiographic disease progression by RANO criteria (see Section 12) during the follow-up period after stopping initial treatment with pembrolizumab and:
 - a. No new anticancer treatment was administered after the last dose of pembrolizumab and
 - b. The participant meets all of the inclusion criteria for lab parameters and performance status
3. The patient EITHER:
 - a. Had stable disease, partial response, or complete response based on RANO criteria and discontinued pembrolizumab after completion of 35 doses (approximately 2 years) for reasons other than disease progression or intolerance or
 - b. Discontinued pembrolizumab after attaining an investigator-determined

confirmed complete response by RANO criteria, received at least 8 cycles of pembrolizumab prior to discontinuation, and received at least 2 treatments with pembrolizumab beyond the date when initial CR was declared

An objective response or disease progression that occurs during the Second Course Phase for a participant will not be counted as an event for the primary analysis of either endpoint in this study.

5.11 Duration of Follow-up

Patients will have one follow-up visit 4 weeks (+/- 1 week) after stopping treatment. They will then be followed for up to 2 years for survival. Routine follow-up will be conducted as per standard of care but is not mandated by this protocol. Patients removed from study for unacceptable adverse events will be followed until resolution or stabilization of the adverse event.

6.0 DOSE DELAYS/DOSE MODIFICATIONS

AEs associated with pembrolizumab exposure may represent an immunologic etiology. These immune-related AEs (irAEs) may occur shortly after the first dose or several months after the last dose of pembrolizumab treatment and may affect more than one body system simultaneously. Therefore, early recognition and initiation of treatment is critical to reduce complications.

Based on existing clinical study data, most irAEs were reversible and could be managed with interruptions of pembrolizumab, administration of corticosteroids and/or other supportive care. For suspected irAEs, ensure adequate evaluation to confirm etiology or exclude other causes. Additional procedures or tests such as bronchoscopy, endoscopy, skin biopsy may be included as part of the evaluation. Based on the severity of irAEs, withhold or permanently discontinue pembrolizumab and administer corticosteroids. Dose modification and toxicity management guidelines for irAEs associated with pembrolizumab are provided in the table below.

General instructions:

1. Corticosteroid taper should be initiated upon AE improving to Grade 1 or less and continue to taper over at least 4 weeks.
2. For situations where pembrolizumab has been withheld, pembrolizumab can be resumed after AE has been reduced to Grade 1 or 0 and corticosteroid has been tapered. Pembrolizumab should be permanently discontinued if AE does not resolve within 12 weeks of last dose or corticosteroids cannot be reduced to ≤ 10 mg prednisone or equivalent per day within 12 weeks.
3. For severe and life-threatening irAEs, IV corticosteroid should be initiated first followed by oral steroid. Other immunosuppressive treatment should be initiated if irAEs cannot be controlled by corticosteroids.

Immune-related AEs	Toxicity grade or conditions (CTCAEv4.0)	Action taken to pembrolizumab	irAE management with corticosteroid and/or other therapies	Monitor and follow-up
Pneumonitis	Grade 2	Withhold	
 • Administer corticosteroids (initial dose of 1 to 2mg/kg prednisone or equivalent) followed by taper. Add prophylactic antibiotics for opportunistic infections 	
 • Monitor participants for signs and symptoms of pneumonitis • Evaluate participants with suspected pneumonitis with radiographic imaging and initiate corticosteroid treatment •
	Grade 3 or 4, or recurrent grade 2	Permanently discontinue		
Diarrhea / colitis	Grade 2 or 3	Withhold	
 • Administer corticosteroids (initial dose of 1 to 2mg/kg prednisone or equivalent) followed by taper 	
 • Monitor participants for signs and symptoms of enterocolitis (i.e. diarrhea, abdominal pain, blood or mucus in stool with or without fever) and of bowel perforation (i.e. peritoneal signs and ileus). • Participants with \geq Grade 2 diarrhea suspecting colitis should consider GI consultation and performing endoscopy to rule out colitis. • Participants with diarrhea/colitis should be advised to drink liberal quantities of clear fluids. If sufficient oral fluid intake is not feasible, fluid and electrolytes should be substituted via IV infusion.
	Grade 4 or recurrent Grade 3	Permanently discontinue		
AST / ALT elevation or Increased Bilirubin	Grade 2 ^a	Withhold	
 • Administer corticosteroids (initial dose of 0.5 to 1mg/kg prednisone or equivalent) followed by taper 	
 • Monitor with liver function tests (consider weekly or more frequently until liver enzyme value returned to baseline or is stable)
	Grade 3 ^b or 4 ^c	Permanently discontinue	
 • Administer corticosteroids (initial dose of 1 to 2mg/kg prednisone or equivalent) followed by taper 	

Type 1 diabetes mellitus (T1DM) or Hyperglycemia	Newly onset T1DM or Grade 3 or 4 hyperglycemia associated with evidence of β -cell failure	Withhold ^d	
 Initiate insulin replacement therapy for participants with T1DM Administer anti-hyperglycemic in participants with hyperglycemia 	
 Monitor participants for hyperglycemia or other signs and symptoms of diabetes.
Hypophysitis	Grade 2	Withhold	
 Administer corticosteroids and initiate hormonal replacements as clinically indicated. 	
 Monitor for signs and symptoms of hypophysitis (including hypopituitarism and adrenal insufficiency)
	Grade 3 or 4	Withhold or permanently discontinue ^d		
Hyperthyroidism	Grade 2	Continue	
 Treat with nonselective beta-blockers (e.g. propranolol) or thionamides as appropriate 	
 Monitor for signs and symptoms of thyroid disorders.
	Grade 3 or 4	Withhold or Permanently discontinue ^d		
Hypothyroidism	Grade 2, 3, or 4	Continue	
 Initiate thyroid replacement hormones (e.g. levothyroxine or liothyroinine) per standard of care 	
 Monitor for signs and symptoms of thyroid disorders.
Nephritis : grading according to increased creatinine or acute kidney injury	Grade 2	Withhold	
 Administer corticosteroids (prednisone 1 to 2mg/kg or equivalent) followed by taper. 	
 Monitor changes of renal function
	Grade 3 or 4	Permanently discontinue		
Neurological Toxicities	Grade 2	Withhold	
 Based on severity of AE administer corticosteroids 	
 Ensure adequate evaluation to confirm etiology and/or exclude other causes
	Grade 3 or 4	Permanently discontinue		
Myocarditis	Grade 1	Withhold	
 Based on severity of AE administer corticosteroids 	
 Ensure adequate evaluation to confirm etiology and/or exclude other causes
	Grade 2, 3 or 4	Permanently discontinue		
Exfoliative Dermatologic Conditions	Suspected SJS, TEN, or DRESS	Withhold	
 Based on severity of AE administer corticosteroids 	
 Ensure adequate evaluation to confirm etiology or exclude other causes
	Confirmed SJS, TEN, or DRESS	Permanently discontinue		
All Other irAEs	Persistent Grade 2	Withhold	
 Based on severity of AE administer corticosteroids 	
 Ensure adequate evaluation to confirm etiology or exclude other causes
	Grade 3	Withhold or discontinue based on the type of event ^e		
	Grade 4 or recurrent Grade 3	Permanently discontinue		

^aAE(s)=adverse event(s); ALT= alanine aminotransferase; AST=aspartate aminotransferase; CTCAE=Common Terminology Criteria for Adverse Events; DRESS=Drug Rash with Eosinophilia and Systemic Symptom; GI=gastrointestinal; IO=immuno-oncology; ir=immune related; IV=intravenous; SJS=Stevens-Johnson Syndrome; T1DM=type 1 diabetes mellitus; TEN=Toxic Epidermal Necrolysis; ULN=upper limit of normal.

Note: Non-irAE will be managed as appropriate, following clinical practice recommendations.

- ^a AST/ALT: >3.0 to 5.0 x ULN if baseline normal; >3.0 to 5.0 x baseline, if baseline abnormal;
bilirubin:>1.5 to 3.0 x ULN if baseline normal; >1.5 to 3.0 x baseline if baseline abnormal
- ^b AST/ALT: >5.0 to 20.0 x ULN, if baseline normal; >5.0 to 20.0 x baseline, if baseline abnormal; bilirubin:>3.0 to 10.0 x ULN if baseline normal; >3.0 to 10.0 x baseline if baseline abnormal
- ^c AST/ALT: >20.0 x ULN, if baseline normal; >20.0 x baseline, if baseline abnormal;
bilirubin: >10.0 x ULN if baseline normal; >10.0 x baseline if baseline abnormal
- ^d The decision to withhold or permanently discontinue pembrolizumab is at the discretion of the investigator or treating physician. If control achieved or \leq Grade 2, pembrolizumab may be resumed.
- ^e Events that require discontinuation include, but are not limited to: encephalitis and other clinically important irAEs (eg, vasculitis and sclerosing cholangitis).

For information on the management of adverse events, see Section 5.7.

7.0 REGULATORY AND REPORTING REQUIREMENTS

The entities providing oversight of safety and compliance with the protocol require reporting as outlined below. Please refer to Appendix B for definitions and Appendix C for a grid of reporting timelines.

Adverse events will be tracked from start of treatment through 30 days following the last day of study treatment. SAEs will be tracked for 90 days following the last dose of study treatment. All adverse events must be recorded on the toxicity tracking case report form. This includes all adverse events:

- belonging to the category “Nervous System Disorders” in the CTCAE version 4.03, regardless of attribution
- experienced by the patient during the administration of MK-3475, regardless of attribution
- that are CTCAE version 4.03 gradable laboratory values, regardless of attribution

The only adverse events that will not be recorded are adverse events that are clearly related to MLA and/or surgery AND ALSO not related to MK-3475.

Refer to the data submission schedule in Section 11 for instructions on the collection of AEs in the EDC.

Reporting requirements for Washington University study team may be found in Section 7.1. Reporting requirements for secondary site study teams participating in Washington University-coordinated research may be found in Section 7.3.

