2.2 Secondary Objectives

1. Phase I: To determine the toxicity profile of MK-3475 in combination with MLA for the treatment of recurrent malignant gliomas.
2. Phase II: To determine the overall survival (OS) of patients with recurrent GBM, WHO grade IV being treated with MK-3475 plus MLA as compared to historical controls treated with MK-3475 alone.
3. Phase II: To assess the anti-glioma immune response before and after MK-3475 with MLA.
4. Phase II: To correlate intratumoral expression of PD-L1 and the frequency of glioma cell-specific cytotoxic T cells with PFS and OS.
5. Phase II: To identify PD-1-dependent biomarkers in glioma cell-specific T cells that negatively correlate with the frequency of glioma cell-specific cytotoxic T cells and PFS and OS.

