15.3 Phase II Stopping Rules

Toxicity will be reviewed on a continuous basis. Early stopping of this trial is calculated based upon the grade 3 seizure rate. It is assumed that a maximum-tolerated seizure rate is 50% and a seizure rate of 33% and or less is acceptable. For each treatment arm (n=20), based on the repeated significance testing (using R function toxbdry) with 80% power and 0.05 overall Type I error, the study will be halted if a treatment-related seizure occurs in the first patient, or both of the first 2 patients, or 3 of the first 4, or 4 of the first 5, or 5 of the first 7, or 6 of the first 9, or 7 of the first 11, or 8 of the first 14, or 9 of the first 16, or 10 of the first 18, or if the 11th treatment-related seizure is observed before the last (20th) patient has completed the trial.

In addition, enrollment will stop and a review will be conducted to determine whether modifications to the protocol are warranted or if the trial should be terminated if 2 patients in either group die or incur life-threatening (grade 4) adverse reactions that are thought to be at least possibly related to study treatment.

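### Section 7.0 both requires and forbids recording some MLA-related adverse events, and never-dosed MLA patients fall outside the toxicity set, so the combination's safety profile can be biased downward

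*Combined protocol and SAP*

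**What the plan says.** **What is recorded (Section 7.0).** Three classes of event are recorded whatever their cause: those "belonging to the category “Nervous System Disorders” in the CTCAE version 4.03, regardless of attribution", those occurring during MK-3475 administration, and gradable laboratory values. The text then names a single exception: "adverse events that will not be recorded are adverse events that are clearly related to MLA and/or surgery AND ALSO not related to MK-3475". The exception has no carve-out for the three classes or for serious events.

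**When recording starts.** Section 7.0: "Adverse events will be tracked from start of treatment through 30 days following the last day of study treatment". It does not say whether treatment starts at MLA or at the first MK-3475 dose. Section 11.1 repeats that start and refers to exceptions in Section 1.0, which is the background section. The calendars in Sections 10.1 and 10.2.1 begin AE assessment at screening.

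**Who is evaluable (Section 5.6).** "All patients who receive any treatment with MK-3475 are evaluable for toxicity". The next sentence reads: "Patients are evaluated from first receiving study treatment until a 30-day follow-up after the conclusion of treatment or death".

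**What the safety data are for.** A phase I secondary objective (Section 2.2, item 1) is "To determine the toxicity profile of MK-3475 in combination with MLA for the treatment of recurrent malignant gliomas". In phase II, Section 15.3 monitors the grade 3 seizure rate. Its boundary begins "the study will be halted if a treatment-related seizure occurs in the first patient". A second rule there stops enrollment for review after two deaths or grade 4 reactions at least possibly related to study treatment.

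**The concern.** The protocol title names the safety and toxicities of MK-3475 combined with MLA as what is being tested. Section 1.4.1 bases the dose escalation on possible edema from both components, and since Amendment 12 every new phase II patient has MLA. A rule that drops one component's events at the point of recording cannot describe the combination. Once an event is unrecorded, later analysis cannot recover it or revisit its attribution.

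Two sites could each follow Section 7.0 faithfully and enter different data for the same post-MLA event. The board that reviews toxicity under Section 13 would then see counts that depend on the reading. If seizures are affected, the phase II halt becomes less sensitive.

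**Working it through.** **Step 1: set the rules side by side.** The right-hand columns show whether an MLA-only event is recorded.

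| MLA-only event | If regardless-of-attribution prevails | If the exception prevails |
|---|---|---|
| Nervous-system category | Recorded | Not recorded |
| Gradable laboratory value | Recorded | Not recorded |
| Other, outside MK-3475 administration | Not recorded | Not recorded |

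The first two rows are the contradiction. The third is a loss on either reading. Of the events that Section 1.2.1 lists after MLA, aphasia and hemiparesis plausibly belong in row 1, hyponatremia in row 2 and deep venous thrombosis in row 3. These placements are assumptions, because the documents do not list the category's terms.

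**Step 2: who falls outside the toxicity set.** Section 5.6 covers anyone who receives MK-3475. A patient whose MLA complication prevents dosing is not covered. Section 5.0 shows another route: a patient biopsied during MLA whose GBM is not confirmed is removed before MK-3475, left out of the enrolled total and replaced. The phase I DLT window (Section 5.5.2) also opens only at the first MK-3475 dose.

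**Step 3: reproduce the seizure rule.** Section 15.3 gives an acceptable rate of 33%, a maximum of 50%, n = 20, stated type I error 0.05 and power 80%. Its clauses are 1/1, 2/2, 3/4, 4/5, 5/7, 6/9, 7/11, 8/14, 9/16, 10/18 and 11/20. Let b(k) be the smallest count r among clauses r/m with m ≥ k. The trial halts at patient k when the cumulative count reaches b(k). For counts x below b(k), the exact recursion is

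P(k, x) = P(k−1, x)(1−p) + P(k−1, x−1)p,

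and probability reaching b(k) is added to the halting total. This gives 38.6% halting at p = 0.33 and 73.1% at p = 0.50. The stated 0.05 and 80% do not reproduce. The 1/1 clause alone halts with probability p, so type I error is at least 33%. Without that clause the figures are 20.5% and 63.2%. This is a separate defect.

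**Step 4: sensitivity to lost seizures.** If a share f of seizures is not counted, the counted rate at a true 50% is 0.5(1−f). The share f is assumed.

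| f | Counted rate | Halting, as printed | Halting, without 1/1 |
|---|---|---|---|
| 0 | 0.50 | 73.1% | 63.2% |
| 10% | 0.45 | 62.3% | 49.0% |
| 20% | 0.40 | 51.6% | 35.5% |
| 1/3 | 0.333 | 39.1% | 21.1% |
| 50% | 0.25 | 26.9% | 9.7% |

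These figures matter only if the exception overrides the nervous-system rule or treatment-related means MK-3475 only, and if the intended target is seizures from either component.

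**The case against.** **Evaluability.** A reader might infer that any patient harmed between MLA and the first dose is lost. Section 5.6 does not support that. A patient harmed after MLA and later dosed is in the set, and evaluation runs from first study treatment, which is not limited to MK-3475. Only never-dosed patients drop out, and the gap from MLA to first dose is about one week.

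**Seizures.** A reader might also infer that seizures are under-counted. The nervous-system rule points the other way, on the assumption that seizure belongs to that category. Moreover, Section 15.3 already filters by attribution. If treatment-related there excludes MLA by intent, MLA-only seizures are outside the rule's target and the thinning model does not apply. Both objections stand.

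**Examples and phase.** The fatal meningitis in Section 1.2.1 was traced to operating-room contamination, so it is not evidence of harm from the ablation itself. The toxicity-profile objective is labelled phase I, and Section 5.2 already reports a phase II dose. New wording therefore cannot by itself repair phase I records. This stands too, although Sections 13 and 15.3 still rely on toxicity data in phase II.

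**Other channels.** Deaths go on a separate form (Section 11.1), secondary sites must notify all serious adverse events (Section 7.2), unanticipated problems are reported (Section 7.1), MLA and Surgery forms exist (Section 11.0), and the second rule in Section 15.3 refers to study treatment rather than MK-3475 alone. These limit the loss of serious events. They do not replace a graded, attributed AE record, and the documents do not describe what the MLA and Surgery forms collect.

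**Conclusion.** The point holds as a contradiction with a limited but definite gap. Section 7.0 gives opposite instructions for MLA-only nervous-system and laboratory events. On either reading, MLA-only events outside the protected classes are not recorded, and MLA patients who never receive MK-3475 are outside the toxicity set. The direction of bias is downward. Its size cannot be derived, because the documents give neither the number of such events nor the number of never-dosed patients.

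The seizure consequence is conditional. The fall from 73% to 52% (20% lost) or 27% (half lost) is a sensitivity range under assumed shares, built on a boundary that does not have its stated error rates. It does not show that the trial under-counts seizures. The plan should be changed because the correction is cheap and unrecorded data cannot be recovered by analysis.

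**What to change.** 1. Section 7.0: delete the exception, and correct the cross-reference in Section 11.1. Record all adverse events from the start of MLA, each attributed to MLA, MK-3475, both or neither. Define the start of treatment for AE recording and align it with the calendars.
2. Section 5.6: report toxicity for all patients who undergo MLA or receive MK-3475, and show MLA-only patients separately, including those removed and replaced under Section 5.0.
3. Section 15.3: state whether treatment-related includes MLA. Reconcile that definition with the boundary rather than adding events to it, since as printed it already halts 38.6% of the time at the acceptable 33% rate. The boundary is also written for 20 patients per arm, while Section 15.4 now plans on 32 subjects in one group.
4. For patients already treated, state in the report which reading each site applied.

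The cost is a wording amendment and some extra AE entries for peri-operative events. Section 5.3 already describes the post-operative neurological checks and laboratory tests that would supply them. The reported toxicity profile may look somewhat less favourable.
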